# 4.2 Exclusion Criteria

- Describe the criteria that define who will be **excluded** in the study as a numbered list. All subjects will NOT meet the following criteria:1) Pre- or post-delivery diabetes
  - 2) Post-delivery hypertension requiring medication

3) Asthma requiring more than occasional use of a sympathomimetic inhaler, but not chronic inhaled steroids

- 4) Inflammatory bowel disease
- 5) Need for any assisted reproductive technologies to become pregnant based on best clinical judgement
- 6) Medical or obstetrical contraindication to the defined exercise program or diet
- 7) Tobacco, excessive alcohol use (greater than 2 drinks/day) or illicit drug use
- 8) Eating disorders such as bulimia
- 9) Gastric surgery to lose weight including banding or bypass procedures

10) Any psychological or psychiatric condition that may impair participation in the lifestyle intervention program

11) Multiple pregnancy

12) HIV, or hepatitis B or C based on patient's history

13) Congenital heart disease unless accompanied by a letter from the subject's cardiologist clearing them to exercise

• Specify whether a study subject may participate in another research study while participating in this research study.

Yes as long as there is no conflict with LIPP as the primary research study.

# 4.3 Withdrawal of Subjects

Subjects who do not become pregnant at the end of the intervention or usual care component (21 months postpartum) are still included in the study. They will not undergo further evaluation but will continue to be followed until either they become pregnant or the study terminates. Contact will be maintained through a brief monthly check-in phone call from study staff. For the intervention arm, this will include a reminder of body weight goal and strategies to sustain weight loss. Testing will resume during pregnancy at the specified intervals of 12-16 and 32 to 36 weeks of pregnancy.

• Describe anticipated circumstances under which subjects will be withdrawn from the research without their consent.

We have had subjects we asked to withdraw from the study because of their not returning for their metabolic assessments in the metabolic research centers, no shows at scheduled training sessions, smoking (which is an exclusion criteria).

If a LIPP subject becomes pregnant prior to 16 weeks after randomization or becomes pregnant before the 3-month postpartum randomization, i.e. no baseline measurement, they would be asked to withdraw.

• Describe procedures that will be followed when subjects withdraw or are withdrawn from the research, including the possibility of partial withdrawal from study intervention with continued data collection.

We will plan to maintain demographic data for subjects who have withdrawn from the study in order to compare with subjects who have been compliant with the study protocol in order to determine if there was bias in subject compliance.

• Include any necessary safety precautions to be applied to subjects who withdraw or are withdrawn (tapering drug doses, evaluative x-ray, etc.). NA

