# 5 Study Design

# 5.1 Study Timelines

- Describe the duration of an individual subject's participation in the study.
  - The time that the subject will be in the study is variable. The minimum time is 13 months (4 months in study and 9 months of pregnancy). The maximum time is 28+ months. The pre-pregnancy component of the study is variable. We list 18 months in study/21 months post-partum but if the subject becomes pregnant after 21 months post-partum, she will be followed in the pregnancy component. Hence, we list 28+ months.
- Describe the duration anticipated to enroll all study subjects at the Tufts study site. Subjects will have their initial testing and randomization 3 calendar months (+/- 3 full weeks) after their delivery. Enrollment begins when the Informed Consent is signed.
- Describe the estimated date for investigators to complete this study (complete primary analyses). The initial grant ended on 11/30/2022 and we are on an approved no-cost extension until 11/30/2023.
- Describe the study procedures that will be accomplished at each study visit. At the HNRCA, CTRC or BWH Research Facility, the following metabolic testing/procedures will be performed:

Metabolic evaluations will be performed at baseline (3 months  $\pm$  3 full weeks postpartum). Follow-up evaluations will be performed after 6 ( $\pm$  3 full weeks) and 9 months ( $\pm$  3 full weeks), 15 ( $\pm$  3 full weeks) and 21 months ( $\pm$  3 full weeks) prior to pregnancy (Figure at the top of the protocol form) up to a maximum of 18 months. Once a subject becomes pregnant and has dating and viability confirmed by ultrasound, metabolic evaluations will continue at 12-16 and 32-36 weeks of gestation. However, if an individual participant has scheduling issues or there are extenuating circumstances with scheduling visits, we may schedule outside of the above windows.

Maternal Body Composition: Anthropometry measurements will include height, weight, and hip and waist circumferences. Total body fat will be measured by whole body plethysmography (Bod Pod; Cosmed, Rome, Italy), (70). We will use a hydration constant of 76% for fat free mass during late pregnancy (71). If a BodPod is not available we will use skin calipers to take skinfold measurements of the triceps and mid-axillary skinfold to estimate body fat.

Resting Energy Expenditure: Resting Metabolic Rate (RMR) will be determined after an overnight fast using the Cosmed OMNIA metabolic cart (Cosmed, Rome Italy) with a

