### 7 Adverse Event Monitoring

#### 7.1 Definitions

• Define adverse events (AEs), serious adverse events (SAEs), and unanticipated problems for your study.

Please refer to the DSMB definitions

During the course of the LIPP study, all adverse events (AEs) and serious adverse events (SAEs) will be monitored, documented, and if causal reported to BWH, TMC and the PBRC and the Data Safety Monitoring Board (DSMB). The Chair of the DSMB will be located at the PBRC. Every attempt will be made to follow a subject who has had negative reaction to any study intervention or procedure.

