#### 7.2 Reporting Procedures

- Describe the protocol-specific reporting procedures, including who will be responsible for each step (e.g., PI, Data Coordinating Center, Medical Monitor), which forms should be completed, timeframes for reporting, how reports will be distributed, and what follow-up is required.
- Include specific details of reporting procedures for:
  - Deaths, life-threatening events, pregnancies PI
  - Other SAEs PI or study coordinator
  - Other AEs study coordinator
  - Other UPs study coordinator All the details are noted in the DSMB charter. The reporting mechanisms are noted above, since different adverse events are reported based on the degree of severity
- Ensure that the reporting procedures meet the reporting requirements of the FDA, NIH, OHRP, sponsor, study leadership and any other regulatory body that applies to the study, as applicable. NIH will receive a yearly non-competitive renewal notice of the progress of the study and any serious adverse events related to the study protocol.

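### Section 4.3 asks women who conceive within 16 weeks of randomisation to withdraw, and nothing in the file provides for collecting how those pregnancies end

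*Combined protocol and SAP*

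**What the plan says.** Section 4.3 states the rule: "If a LIPP subject becomes pregnant prior to 16 weeks after randomization or becomes pregnant before the 3-month postpartum randomization", she would be asked to withdraw. This point concerns the randomised women only.

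The protocol template then asks what happens on withdrawal, "including the possibility of partial withdrawal from study intervention with continued data collection". The reply is "We will plan to maintain demographic data for subjects who have withdrawn from the study", for a comparison with compliant subjects to look for bias. The next item, on safety precautions for withdrawn subjects, is answered as not applicable.

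Other sections touch on the subject:

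- Section 5.1 gives a minimum participation of 13 months, made up of 4 months in study and 9 months of pregnancy.
- Section 7.1 says: "During the course of the LIPP study, all adverse events (AEs) and serious adverse events (SAEs) will be monitored, documented, and if causal reported". It also promises an effort to follow anyone who reacts badly to an intervention or procedure. Its list of expected events includes miscarriage, preterm delivery, stillbirth, low birth weight and birth defects, and says these are collected as outcomes.
- Section 7.2 assigns reporting responsibility: "Deaths, life-threatening events, pregnancies PI". It adds: "All the details are noted in the DSMB charter".
- Section 8.1 names SGA birth and preterm delivery as safety outcomes to be watched in the intervention group, and calls the risk theoretical.
- Section 4.3 keeps women who are not pregnant at 21 months postpartum in the study: "Contact will be maintained through a brief monthly check-in phone call from study staff".

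**The concern.** A woman who conceives in the first 16 weeks has been randomised, and in the intervention arm she may have been in the active weight-loss phase around conception. Section 2.2 describes a deficit of 500 kcal/day, and section 5.1 describes 12 weeks of exercise on 3 to 5 days a week, with no pregnancy test required at each session. Section 3 gives the investigators' own reason for caution: they have reported more SGA babies among obese women who lost weight or gained too little in pregnancy.

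These pregnancies may therefore lie closest to the exposure that motivates the safety outcome in section 8.1. Under section 4.3 the woman leaves the study, and the section does not say that anyone learns whether she miscarried, delivered early or had an affected baby. The DSMB may hear that a pregnancy occurred without hearing how it ended. The stake is the completeness of the safety data, not the efficacy result.

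**Working it through.** **1. Where the 16-week limit falls** (30.44 days per month). Randomisation at 3 months is day 3 × 30.44 = 91.3 postpartum. Adding 16 × 7 = 112 days gives day 203.3, or 203.3 / 30.44 = 6.68 months. This fits the plan's own minimum: 112 / 30.44 = 3.68 months, which section 5.1 rounds to 4.

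**2. Whether the contraception instructions cover the window.** Contraception is an inclusion criterion (section 4.1), but two durations are given.

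- Section 5.2, at least 7 months: day 7 × 30.44 = 213.1. Margin to the limit: 213.1 − 203.3 = 9.8 days to spare.
- Section 2.2, until the 6-month visit is done: day 6 × 30.44 = 182.6. Shortfall: 203.3 − 182.6 = 20.7 days.

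**3. Whether the uncovered days overlap the supervised phase.** The phase lasts 12 weeks and ends on day 91.3 + 84 = 175.3. Both instructions outlast it, by 182.6 − 175.3 = 7.3 days and 213.1 − 175.3 = 37.8 days. The 20.7 uncovered days in step 2 therefore come after the supervised phase.

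**4. Shifted dates.** Section 5.1 allows 3 weeks either side of each visit.

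- Randomised 21 days late: supervised phase ends day 196.3, limit day 224.3. The section 5.2 instruction (day 213.1) still covers the phase but stops 224.3 − 213.1 = 11.2 days before the limit. The section 2.2 instruction, with the 6-month visit on its nominal date, stops 196.3 − 182.6 = 13.7 days before the phase ends.
- Randomised on time, 6-month visit 21 days early (day 161.6): the section 2.2 instruction stops 175.3 − 161.6 = 13.7 days before the phase ends and 203.3 − 161.6 = 41.7 days before the limit.

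**5. Whether any section supplies the outcome.** Read side by side:

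- Section 7.2 covers reporting that a pregnancy occurred. Outcome is not mentioned there, and the details are referred to the charter.
- Section 7.1 covers events during the study and follow-up after a bad reaction. Its list of expected pregnancy events neither includes nor excludes withdrawn women. Its relatedness time courses run from 1–4 to 24–48 hours around fasting or the glucose test, so they fit a later pregnancy loss poorly.
- Sections 4.4.2 and 5.1 (delivery chart data), 6.5 (record access for the outcome pregnancy) and 8.1 (SGA and preterm delivery) are all general. None mentions women withdrawn for early conception.

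**6. What a change could still reach.** The version is dated 31 March 2023 and the no-cost extension ends 30 November 2023 (section 5.1), 244 days later. A conception on the version date would be at 244 + 14 = 258 days, or 36 weeks 6 days, when the extension ends. Its 40-week date, 266 days after conception, is 22 December 2023. A birth by 30 November 2023 needs conception by 30 March 2023 for 37 weeks 0 days, and by 9 March 2023 for 40 weeks 0 days.

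**The case against.** The strongest reply is that the gap lies where the protocol hands over to a document that cannot be seen. The template for section 7.2 asks what follow-up is required, and the answer is to see the DSMB charter. The consent pages, where record access after withdrawal would normally be set out, are not in the file either. This stands: the absence can be asserted only for the file as it is.

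A reader might infer that the plan discards these outcomes, or that the safety tables will certainly describe only later conceptions. The documents do not support that. Section 4.3 says that demographic data are kept and does not say that everything else is dropped. Section 7.1 commits to collecting pregnancy events and makes no exception for withdrawn women. The supportable statement is that the safety data could omit these pregnancies.

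A reader might also infer that the uncovered contraceptive window exposes women to the supervised phase. On the nominal schedule it does not (step 3 of the working). Overlap then needs contraceptive failure or non-use, or else shifted dates combined with the shorter instruction.

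Two supporting comparisons carry little weight. The 13-month minimum restates the 16-week rule and says nothing separate about data collection. The monthly calls after 21 months keep women who may still contribute the study pregnancy, so they show that light contact is feasible but are not a precedent for safety follow-up after withdrawal.

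**Conclusion.** The concern holds in limited form. Section 4.3 states a rule for these women, and nothing visible provides for learning how their pregnancies end. Followed as written, the SGA, preterm and pregnancy-loss data could leave out some randomised pregnancies, a few of which may overlap active weight loss.

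The numbers are probably small, because contraception is required at entry. The documents give no conception rate for this period, so no count can be supported. A few such pregnancies could not settle the SGA question. The primary comparison is not touched.

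The conclusion assumes that the charter and consent form add no outcome rule. If either does, only a cross-reference is missing. It also reads the section 4.3 rule as applying to both arms, which fits because the same sentence covers women not yet randomised. This is a low-cost improvement to consider, held with medium confidence.

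**What to change.** Keep the withdrawal from intervention and study visits, and add to section 4.3:

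> Randomised women in either arm who conceive before 16 weeks stay, with their consent, in safety follow-up by medical-record review to the end of pregnancy (loss, gestational age, birth weight and SGA status, congenital anomaly, neonatal death). These outcomes are reported by randomised arm to the DSMB and in the final safety tables.

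If the DSMB charter already requires this, cite it in section 4.3 instead.

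The cost is one protocol sentence, a consent line on record access after withdrawal, chart abstraction for a few women, and re-contact and consent of any women already withdrawn. No visit is added. Boston staff already abstract maternal and infant charts at delivery (sections 4.4.2 and 5.1), and Pennington already uses a medical release form (section 11.1). Whether that access survives withdrawal is not stated.

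Some women will decline or deliver elsewhere. Reach within current funding is also limited: by 30 November 2023 the change would capture early losses, preterm births and pregnancies already under way, while term outcomes of conceptions after about March 2023 would need record review after that date.

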#### 4.4 Recruitment and Retention

# 4.4.1 Local Recruitment Methods

Describe the following attributes of the recruitment plan for the local Tufts site:

- When, where, and how potential subjects will be recruited.
- We plan to approach subjects, assuming they and their newborn are stable, on the postpartum unit of Tufts Medical Center (Tufts MC) after their delivery. The PI and/or

the study coordinator will inform the subjects about the study. Subjects will be identified as being eligible based on information obtained at the time of their delivery. Potential subjects will be interviewed by the PI and/or the study coordinator to determine eligibility and potential interest in the LIPP project. They will be given a brochure describing the study. If potentially interested we will obtain contact information, such as email and phone numbers and contact potential subjects prior to their 4-6 week postpartum visit. Before their postpartum visit with their OB health care provider, study staff will contact them to determine if they might be interested in participating in the LIPP study. If they are, one of the recruiters will meet the subject at their postpartum visit, explain the study in more detail, and provide the potential subject with a copy of the consent form. The subjects will have until 3 calendar months (+/- 3 full weeks) to decide to join the study and be scheduled for metabolic testing. We created an IRB-approved informational website that is linked to on the MIRI lab page at Tufts MC and distributes ads via social media and print linking to the informational website. If a potential participant would like to ask questions related to the study to a current or former participant, LIPP study staff will initiate this communication (via email, text or phone call) with the approval of both individuals.

- *Source of subjects (for example, patient population, local community, etc.).* Postpartum patients at TMC.
- *Methods that will be used to identify potential subjects.* Review of EMR charts. Patients who are found to meet exclusion criteria during screening, such as history of HIV, or hepatitis B or C, will not be recruited and their PHI will not be recorded.
- *Materials that will be used to recruit subjects.* Primarily brochures and speaking with potential subjects, as well as sharing the study website page with those who are interested. The brochure will be given to all potential subjects until we have reached our recruitment goals.
- When subjects respond to recruitment material, describe the information that will be provided to them about the study and the information that will be collected from subjects (e.g. name, telephone number, etc.) or submit a telephone/email script that will be used. We do not use a script. Subjects will be given a copy of the brochure and if interested will be given a copy of the consent form to be reviewed with the study coordinator.
  - If data will be retained for subjects that are determined to be ineligible, specify how privacy and confidentiality of these potential subjects will be maintained. Data will be retained until the primary manuscript is written noting differences in the study population that have determined to be ineligible for whatever reason based on inclusion/exclusion criteria.
  - *Also, submit the screening log to the IRB for review.* The screening log template has been submitted with the application.
  - We will retain non PHI information number of subjects etc. who are determined not to be eligible.
  - Please refer to the DSMB reports we have submitted.
- If recruitment material is being mailed or otherwise distributed, describe where/how, the distribution list will be obtained. The information will be given to potential subjects at the time of the postpartum visit. The same brochure will be sent via email to potential subjects prior to their postpartum visit to remind them of the specifics of the LIPP study.
- Specify how and why the listed recruitment methods will be effective in attracting the targeted subject population.

The recruitment methods have been successful in recruiting the first 20 subjects in Cleveland at MetroHealth Medical Center.

# 4.4.2 Study-Wide Recruitment Methods

# Is this is a multicenter study where subjects will be recruited by methods not under the control of the local Tufts site (e.g., call centers, national advertisements)?

# 🗹 Yes 🛛 No

If **Yes**, describe the following:

• Methods of recruitment not under the control of the local Tufts site.

There will be no further recruitment at the Pennington site in Baton Rouge; we will continue to follow subjects until they deliver at the PBRC (please see section 11.1 for site specific information). There will also be no further recruitment at Massachusetts General Hospital (MGH) but recruitment will occur at Brigham and Women's Hospital (BWH) in Boston in coordination with TMC. Potential participants in the Lifestyle Intervention in Preparation for Pregnancy (LIPP) study will be recruited from eligible women who have delivered infants at BWH. Women will be approached on the Labor and Delivery and Postpartum units of BWH following delivery of their infant following a screening of medical records for exclusions including entering restrictive charts ('breaking the glass'). Women who express interest will be given an IRB approved flyer and contact information will be collected. Contact information will be transferred to Tufts study staff via a Mass General Brigham maintained secure Dropbox. Tufts study staff will reach out by email, phone, or mail to women who agree to be contacted and will offer study participation. As an alternative to in-person recruitment, women who are missed in-person will receive a letter via the Mass General Brigham patient portal with an opt-out option. If women do not opt-out, the LIPP study staff will contact them in 3-4 weeks via email or phone number by way of the listed contact information in their medical records. All subsequent study procedures will be conducted at TMC and BWH for those women who elect to participate. For women who deliver at MGH or BWH, delivery protocol will be followed accordingly for each site. At the time of delivery, LIPP study staff from all Boston-area sites (MGH, BWH and TMC) will collect study sample data, maternal and infant data from medical charts, and conduct maternal questionnaires.

- *When, where, and how potential subjects will be recruited.* Brigham and Women's Hospital (BWH) in Boston, MA.
- *Methods that will be used to identify potential subjects.* Similar to what we will use at Tufts. Data will be provided if requested and have IRB approval.
- Materials that will be used to recruit subjects. Submit a copy of each recruitment-related document with the application. For advertisements, attach the final copy of the print advertisement. When advertisements are audiotaped or videotaped for broadcast, attach the final audio/video. You may submit a script of the proposed audio or video advertisement for IRB review before taping the final version in case revisions are requested. Once recommended changes are made, the final version is to be submitted to the IRB for review and final approval.

# 4.4.3 Payment

Will subjects receive money, gifts, or any other incentive for participating in this study? *This does not include reimbursement for expenses, which is considered in the next section.* 

